7.4 Questionnaires (2 week, 4 month and 18 month approximate time points)

7.4.1 Socio-demographic data

For an example please see Appendix

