It is well known that sleep is essential for brain development and maturation. Studies have shown that sleep-deprived young animals have smaller brains with loss of brain plasticity, which leads to diminished learning and adverse long-term behavioural effects. It is also established that infant massage improves sleep hygiene and is linked to the theory of environmental enrichment, which promotes brain development. Brain development during the first years of life depends on the quality of stimulation in the infant's environment. Early child development is a life-long determinant of health and well-being. There are significant societal and economic benefits from optimal infant cognitive development (2).

Protocol/Sponsor Number: GB02/17UCC Principal Investigator: [name]

5 Trial Objectives and Purpose

Primary objective

To assess the effect of a structured sensory enrichment programme on Infant sleep using qualitative and quantitate measures.

Secondary objective

To assess the effect of a structured sensory enrichment programme on neuro-development as assessed by a standardised neurodevelopmental assessment at approx. 4 months and approx. 18 months of age.

6 Description of protocol methodology

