6.2 Subjects

A total of 200 full term healthy infants will be studied. Recruitment will take place at CUMH and UCL-ICH London.

Inclusion criteria for participant selection are:

- Infants born > 37 weeks gestation
- Single births
- Not requiring admission to the Neonatal Unit
- Healthy infants without suspected congenital or metabolic anomalies

Exclusion criteria for participant selection are:

[figure not shown]
- Infants born < 37 weeks gestation
- Multiple births

Page 6

• Severe metabolic or genetic anomaly that would require ongoing specialist care in the infancy period.

Admission to the Neonatal Unit.6.2.1 Figure 1 Flow chart design of study

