7.3 Sensory enrichment programme including infant massage

A total of 200 full term healthy infants will be recruited. Recruitment will take place at CUMH and UCL-ICH London. Parents will be invited to provide proxy consent for their infant to participate and also for their own participation in the BabySMART study.

Once Day 2 screening assessment is complete, parents will be informed that the next appointment will be in approximately 2 - 3 weeks and that a member of the BabySMART team will contact them to schedule this appointment. Randomisation will occur at this visit. Participants will be randomised to either a structured sensory enrichment programme including infant massage (intervention arm) or to the control arm.

The massage will be applied according to IAIM (International Association of Infant Massage). Created in 1976 by Vimala McClure, it is the first global organisation with a professional programme which is run in several countries around the world, due to its proven benefits. The purpose of IAIM is to create a nurturing touch and communication through training, education and research so that parents, caregivers and children are loved, valued and respected throughout the world community.

At the 2 week visit parents will be provided with training in infant massage by an instructor who has completed a Baby Massage Ireland trainer course. The massage should be carried out daily until the 4 month visit. Massage training will be completed on-site in the INFANT Research Centre in the new Paediatric unit in the CUH and the JOHNSON'S® HEAD-TO-TOE® extra moisturizing baby cream will be supplied at these appointments

Mothers will be informed about the enrichment programme which will include the benefits of baby massage, infant cues, duration of application, points of care for application and application technique at this stage. The technique of massage application will be shown to the mother by the researcher using a model baby (doll).

Mothers will be asked to apply the massage on their own baby as instructed and they will be observed to determine whether they applied the massage correctly or not. Training will be reinforced both at the training session and by the provision of a training DVD which will be provided to parents.

Baby massage education will also be given at drop in classes where a review of the strokes will be undertaken. Each parent's application of baby massage will be observed and evaluated for correct

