7.5 MiChild Mobile Application

MiChild is a mobile application which is to be used by registered users only for the capture, storage and analysis of sleep and feeding. The aim of this app is to provide researchers working on the BabySMART study with a view of key infant data from birth to 4 months. The application is not mandatory and the parents can choose to record the information in a paper format in the diary that has been designed for the study. MiChild will provide a data capture tool where parents can capture in real time details on infant sleep, adherence and acceptance of the sensory enrichment programme and limited feeding data. The data inputted by parents will be available to them in an aggregated view allowing them to review weekly sleep and feeding.

This secure, multi-platform (Android & iOS) mobile solution will provide parents/guardians with the ability to capture an accurate and real-time view of their infant's sleep and feeding from birth. As well as the above, the application will also allow communication between parents and BabySMART research staff via a messaging option.

This application will be available through the apple app store and google play store. The application will only be accessible to parents who have a registered account created by research staff working on the BabySMART Study.

Registered users of the app will be created by research staff with the necessary privileges through an administrative application. These registered users will be provided with a random password by the BabySMART research staff at time of registration. This password will be stored in the database encrypted using industry standard Advanced Encryption Standard – Cipher Block Chaining (AES-CBC) which will have a 256-bit key for encryption. The registered user of the app will have to enter a "MiChild" user ID which is unique to the app and is created by the BabySMART research staff. This ID combined with their password allows a user's access to the application. At any stage throughout the use of the application, clinical staff can deactivate an account and therefore render the app un-usable by the users.

All data will be stored in University College Cork, on University College Cork servers. These servers will have restricted access to INFANT IT personnel only. All data on these servers will have restricted access insofar as it will be restricted to BabySMART research staff only so as to protect patient confidentiality.

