Daily/Almost Daily A few times per week Once a week Less than once a week	
19. How many, on average each day?	
20. Do you allow smoking in your house?	
No Yes, occasionally Yes, regularly Yes, e-cigarettes only	
21. Is your baby exposed to smoking outside the h	ome (eg. grandparents?)
No Yes, occasionally Yes, regularly Yes, e-cigarettes only	
22. Where does your baby usually sleep?	
Cot in your bedroom	
Cot in their own bedroom	
We share a bed	

23. Does your baby ever	sleep in bed with	you?	Yes		No	
24. If yes, is it for the	Whole night Part of the nig	ht				
25. If yes , how often doe	es this occur	Every night				
		4-6 times per v 2-3 times per v Once a week Rarely				
26. How often do you th	ink a new-born ba	by should sleep	in a 24		od?	
			Hours			
27. Where do you seek a that apply)?	ndvice regarding yo	our new-borns sl	leeping	and feedi	ing hal	oits (tick all
Books						
Internet						
Parents/Grandparen	ts					
Paediatrician/GP						
Friends						
Other						
28. Do you follow any 'N Yes No	1ummy Bloggers'?					
29. If Yes, who?						
30. How often do you ba	ith your baby?					
Once a week 2-3 times a week						

4-6 times a week Daily	
Other, please specify	
31. What do you use in the bath?	
Please specify product name and brand 32. How often do you moisturise your baby	
Never Occasionally	
Once a week	
2-3 times a week	
Daily/Almost daily	
Several times a day	
33. What do you use to moisturise your baby's skin?	\neg
Please specify product name and brand	
Feeding	
34. How are you feeding your baby?	
Breast fed	
Infant Formula	
Both	
35. How many feeds do they get on average in 24 hours?	
Breast-milk	
Infant formula milk	
36. Is your baby fed on a regular schedule eg. every 4 hours?	
Yes, always	
Yes, try to	
No, fed on demand	
37. Does your baby use a soother/dummy?	
Yes, regularly	
Yes, occasionally	
No	
Baby's Health	
38. Has your baby been unwell or needed to visit your GP (since leaving hospital)?	
Yes	
No No	
39. Did your baby require any treatment or follow up (since birth)?	

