Is your baby fed on a regular schedule eg. every 4 hours?
Yes, always
Yes, try to

No, fed on demand	
If giving solid foods, how old was he/sh	he when they first had solids?
Age (weeks)	
Have you given your baby any vitaming	s or supplements since your last visit?
Yes	
No	
If yes, please provide details	
Does your baby use a soother/dummy	?
Yes, regularly	
Yes, occasionally	
No	
Sleeping	
Sleeping Arrangements	
Infant cot in separate room	
Infant cot in parent's room	
In parent's bed	
Infant cot in room with sibling	
Other, please specify	
Sleeping Position	
On his / her belly	
On his / her side	
On his / her back	
Sleeping time during the day (between	າ 7am and 7pm)

Protocol/Sponsor Number: GB02/17UCC Principal Investigator: [name]

Hours

Sleeping time during the night (between 7pm and 7am) Hours
How long does it take to put your baby to sleep in the evening? Hours Minutes
Wakefulness time between 10pm and 6am Hours
How does your baby fall asleep?
While feeding
Being rocked
Being held
In bed alone
In bed near parent
When does your baby usually fall asleep at night (24 hour format)? Time
Do you consider your baby's sleep a problem?
A very serious problem
A small problem
Not a problem
Is it always the same person that puts the baby to bed?
Yes
No

If yes, who is it?	
Mother	
Father	
Other person	
Does the baby move in his/her sleep? Yes No	
The things that disturb my baby's sleep are: (tick a	ill that apply)
Any sound, even very soft sounds	
Radio or TV	
People talking	
Phone ringing	
Other	
Nothing disturbs my baby's sleep	
When my baby wakes up he/she is usually:	
Fussy	
Crying	
Hungry	
Alert but quiet	
Alert and active smiling when I app	proach
Other	
My baby can help calm him/herself to sleep by:	
Sucking on thumb or fingers	

	Holding a favourite blanket or soft	toy		
	Sucking on a soother/dummy			
	Other			
When my baby	needs help at night to calm down Pick him/her up	l:		
	Try talking and gently rubbing his/	her back		
	Play music for him/her			
	Let him/her cry before I go in			
	Give him/her a soother/dummy or	a bottle		
	Other			
I feel the best way to help my baby sleep through the night is to:				
	Stick to the same bedtime routine			
	Feed my baby shortly before putti	ng him/her	to bed	
	Let my baby cry him / herself to slo	еер		
	Comforting my baby whenever it's	needed		
	Nothing I do seems to help			
	Other			
Do you know w	hat sleep training is?			
	Yes			
Have you tried	sleep training?			
	Yes, The Cry it Out approach			

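### The parent-reported sleep items asked at 4 and 18 months are not in the 2-week questionnaire, so they have no same-instrument baseline

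*Combined protocol and SAP*

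**What the plan says.** The primary objective (section 5) is "To assess the effect of a structured sensory enrichment programme on Infant sleep using qualitative and quantitate measures". It names no instrument, endpoint or time point. Section 6.1 describes the study as unblinded, and section 6.2 gives its size: "A total of 200 full term healthy infants will be studied".

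Sleep is measured in three ways:

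- **Sleep EEG** (section 7.2): once, at about 4 months.
- **MiChild app or paper study diary** (section 7.5): parent-recorded sleep from birth to 4 months. On the app the text says "The application is not mandatory"; parents may use the paper diary instead.
- **Questionnaires** (section 7.4): "7.4 Questionnaires (2 week, 4 month and 18 month approximate time points". Sections 7.4.1 and 7.4.2 refer to the appended forms as examples.

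The 4-month form in the Appendix has a Sleeping block that includes "Sleeping time during the night (between 7pm and 7am"), together with day sleep, settling time, wakefulness from 10pm to 6am and a rating of whether sleep is a problem. The 18-month form repeats these items. The 2-week form has an item "22. Where does your baby usually sleep", then bed-sharing (items 23-25), how much the parent believes a newborn should sleep (item 26) and sources of advice (item 27).

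Of the visit 2-3 weeks after the Day 2 assessment, section 7.3 says "Randomisation will occur at this visit". Massage training is also placed at the 2-week visit.

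**The concern.** Infant sleep is the subject of the primary objective, yet the 2-week form never asks how the infant sleeps. This departs from the plan's own practice. Trans-epidermal water loss is measured at Day 2 and 4 months, and anthropometry at 2 weeks, 4 months and 18 months. Bathing, moisturising, soother use and maternal quality of life are asked at all three questionnaire visits.

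Without a value before allocation, chance imbalance in reported sleep or settling cannot be seen on this instrument, and the later comparisons cannot be adjusted for it. The gap is widest at 18 months, because the EEG is done only at about 4 months and the app record ends at 4 months.

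A related point is visit order. The questionnaire, randomisation and massage training share one visit, and the prose gives no sequence. In an unblinded study, parent-rated answers given after allocation is known could not serve as a clean baseline. A baseline missed before allocation cannot be recovered later.

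**Working it through.** **1. Item comparison across the appended forms**

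| Item | 2 weeks | 4 months | 18 months |
|---|---|---|---|
| Day sleep, 7am-7pm | no | yes | yes |
| Night sleep, 7pm-7am | no | yes | yes |
| Time to settle in the evening | no | yes | yes |
| Wakefulness, 10pm-6am | no | yes | yes |
| Sleep a problem (three categories) | no | yes | yes |
| Total | 0 of 5 | 5 of 5 | 5 of 5 |

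The numbering of the 2-week form runs to 49 with no gap where a sleep block could have been lost, so this is not a text-extraction fault.

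**2. Could the diary supply the baseline?** Section 6.3 has mothers approached usually within 48 hours of delivery and the consent-day assessment ideally on day 2. Randomisation follows at a visit about 2-3 weeks later. Recording that starts soon after consent would therefore precede allocation, and could give a baseline for diary outcomes up to 4 months. The text states no pre-randomisation window and no minimum completeness. The app screenshots are not available here, so whether the diary items match the questionnaire items cannot be checked.

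**3. Size of the loss.** The documents give no power calculation, allocation ratio, standard deviation or correlation, so there is no figure to reproduce. Only the 200 infants come from the plan. Assumed: 1:1 allocation (100 per arm), all 200 analysed, two-sided 5%, 80% power, and a correlation r between the 2-week and later value.

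- Share of variance removed by adjustment = r².
- Equivalent sample size = 200/(1 − r²).
- Detectable difference, unadjusted = (1.960 + 0.842) × √(2/100) = 0.396 SD. Adjusted = 0.396 × √(1 − r²).
- Power is for a true difference of 0.40 SD. Unadjusted it is 80.7%.

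| r | Variance removed | Equivalent n | Detectable difference (SD) | Power |
|---|---|---|---|---|
| 0.1 | 1% | 202 | 0.394 | 81.1% |
| 0.2 | 4% | 208 | 0.388 | 82.3% |
| 0.3 | 9% | 220 | 0.378 | 84.3% |
| 0.5 | 25% | 267 | 0.343 | 90.4% |

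**4. Chance imbalance.** The SD of the baseline difference between arms is √(2/100) = 0.141 SD. In about 1 trial in 20 it exceeds 1.96 × 0.141 = 0.277 SD. It carries through to the outcome only after multiplication by r: 0.277 × 0.2 = 0.06 SD, and 0.277 × 0.5 = 0.14 SD.

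**The case against.** A reader might infer that the primary objective itself has no baseline. The documents do not support that. The objective names no instrument, nothing declares the questionnaire the primary sleep measure, and parent-recorded sleep is planned from birth. The optional status applies to the app, since the paper diary is offered in its place. Nor would the added items give the EEG a baseline, as they are on a different scale.

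A reader might also infer that the treatment comparison is biased, or that change in sleep cannot be described. Neither follows. Randomisation protects the unadjusted comparison, and its standard error already allows for chance imbalance. Change from 4 to 18 months can be described from the repeated block, and the diary covers birth to 4 months.

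The gain from adjustment rests on an assumed r. At r = 0.1 to 0.3 the detectable difference falls by less than 0.02 SD. On visit order, the study flow chart is not shown and may settle the sequence, so it cannot be said that parents would answer after learning their arm. Many 2-week items, such as education or income, would hardly shift in any case. Finally, the forms are called examples.

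All of this stands, and it limits the point to the questionnaire items and to a modest loss. It does not remove the gap at 18 months or supply a stated diary window.

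**Conclusion.** The point holds for the questionnaire. Five parent-reported sleep items asked at 4 and 18 months have no same-instrument value before allocation, and at 18 months no other sleep measure is described. The loss is a balance check and some precision: about 1-9% of variance for r of 0.1-0.3, up to 25% at r = 0.5, with r and 1:1 allocation assumed. The validity of the randomised comparison is not in question. The finding assumes that the forms in use match the appended examples. It is a modest weakness, worth correcting because the correction is cheap and the opportunity ends at allocation.

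**What to change.** - Add the five items to the 2-week questionnaire, worded as in the 4-month form.
- State in sections 7.3 and 7.4 that the 2-week questionnaire is completed before allocation is revealed and before massage training, unless the flow chart already says so.
- Specify the 2-week values as covariates for the corresponding 4- and 18-month questionnaire sleep comparisons. The sleep-problem item is a three-category rating and should enter as a categorical covariate.
- For diary outcomes, define a pre-randomisation diary window with a completeness rule, and use sleep in that window as the covariate.

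The cost is a few minutes of parent time at an existing visit and a few sentences in the plan, with no extra visit or staff. The downside is that newborn sleep may predict later sleep only weakly, in which case the gain in precision is small and the balance check is the main return.

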7.4.2 Baby's household and health

For an example please see Appendix

7.4.3 Mothers postnatal depression questionnaire & parental attachment style – approximately 4 month time point only

The survey contains questionnaires that are directed at screening for postnatal depression, identifying the attachment type of the parent and evaluating the growing relationship between the mother and infant.

The Maternal Postnatal Attachment Theory questionnaire (MPAS; Condon & Corkindale, 1998) captures different sorts of emotional reactions parents have when caring for young babies. Of particular interest to this study is the mother's attachment style to the infant. (Please see Appendix) Postnatal depression scores will be measured through the Edinburgh Postnatal Depression Scale (EDPS; Cox, Holden & Sagovsky, 1987). This questionnaire will be utilized as a screening tool for postnatal depression. (Please see Appendix).

It is estimated that up to 1 in 7 new mothers will experience postnatal depression (PND) (Health Service Executive, 2008). It is therefore expected that a similar percentage of mothers in this study will have escalated scores on the EDPS. It is imperative that a referral pathway be identified to ensure the women obtain a comprehensive follow up if their scores indicate they are at risk of PND. Mothers who have an escalated score on the EDPS (score >10) or who have an escalated score in the anxiety subscale of the EDPS (scores > 6) or who have answered positively to the suicidal risk question (Scores > 0) will all receive follow up. As recommended by the EDPS any participant with an escalated score will be given the EDPS to complete again after two weeks. Participants who remain in the moderate range (score 10-13) after completing the EDPS for the second time will be strongly advised to consent to a GP referral, while participants exceeding this threshold and scoring in the high risk threshold (score 13-30) will be automatically referred to their GP.

Protocol/Sponsor Number: GB02/17UCC Principal Investigator: [name]

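### Section 7.4.3 ties its GP actions to the repeat depression total alone, so a mother still positive on self-harm or anxiety with a total below 10 has no stated action, and staff are given none for the day of a positive self-harm answer

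*Combined protocol and SAP*

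**What the plan says.** The heading of section 7.4.3 places the Edinburgh scale (EDPS in the protocol) at the "approximately 4 month time point only". The section states its own standard: "It is imperative that a referral pathway be identified to ensure the women obtain a comprehensive follow up".

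Three criteria bring a mother into follow-up:

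- Total: "Mothers who have an escalated score on the EDPS (score >10".
- Anxiety: "an escalated score in the anxiety subscale of the EDPS (scores > 6".
- Self-harm: those who "answered positively to the suicidal risk question (Scores > 0) will all receive follow up".

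The next step is that "any participant with an escalated score will be given the EDPS to complete again after two weeks". Two end actions follow. The first concerns "Participants who remain in the moderate range (score 10-13) after completing the EDPS for the second time", who are urged to agree to a GP referral. The second is that "participants exceeding this threshold and scoring in the high risk threshold (score 13-30) will be automatically referred to their GP".

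On the form itself (Appendix, 4-month questionnaire, Edinburgh score, item 10), a note addressed to the mother asks her to tell the team that day if she has thoughts of self-harm. It contains no instruction to staff.

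**The concern.** By listing anxiety and self-harm as separate triggers, the section accepts that a mother can need attention without a high total. Those two triggers are then not mentioned again. Once the scale has been repeated, only the total decides whether a GP becomes involved. A mother who was flagged because of a self-harm answer can give the same answer at the repeat and meet no rule at all.

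The study asks a direct self-harm question and so must expect some positive answers. What is at stake is participant safety and the section's own aim of a comprehensive pathway. Randomisation, endpoints and analysis are not involved.

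**Working it through.** **1. Score range.** The form has 10 items with four options each (Appendix, 4-month questionnaire), and section 7.4.3 gives 30 as the top of the scale. 30 / 10 = 3, so each item runs 0 to 3 and the total runs 0 to 30.

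**2. The rule applied to each total.**

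| Total | Flagged at first screen by total alone (above 10)? | Action stated if this is the repeat total |
|---|---|---|
| 0–9 | No | None |
| 10 | No | Urged to agree to GP referral |
| 11–12 | Yes | Urged to agree to GP referral |
| 13 | Yes | Both actions apply |
| 14–30 | Yes | Automatic GP referral |

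**3. Can a mother positive on self-harm fall in the row without an action?** Positive means item 10 is at least 1, so the total is at least 1. With item 10 = 1 and the other nine items summing to 0, 1, …, 8, the total is 1, 2, …, 9. Every total from 1 to 9 is possible.

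**4. Can a mother positive on anxiety?** Above 6 means at least 7. The documents do not list the subscale items; assume the subscale is a plain sum of form items. The total is then at least 7. With a subscale score of 7 and the remaining items summing to 0, 1 or 2, the total is 7, 8 or 9.

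**5. What happens to a mother positive only on self-harm?** The wording allows two readings. The repeat is for a participant with an escalated score, a phrase the section uses for the total and the anxiety subscale; for the self-harm item it speaks of a positive answer.

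- If an escalated score covers all three triggers, her first concrete step in 7.4.3 is the repeat after two weeks, and step 3 then applies.
- If it covers only the first two, she is promised follow-up, but no concrete step is described.

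Neither reading supplies an end action for a total below 10, or a staff action on the day.

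**6. Does anything else visible close the gap?**

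- Section 6.3 plans the next visit after 4 months at about 18 months, 18 − 4 = 14 months later, and the scale is not given then.
- The follow-up statements in section 7.2 (EEG) and section 7.1.5 (Griffiths) concern findings in the infant.
- The note at item 10 relies on the mother to speak up. It does not ask staff to look at the answer, and does not say what they should do.

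**7. Boundaries.** Score 13 belongs to both bands. The phrase about exceeding the threshold suggests that 13 was meant as moderate, so the conflict is one point wide and concerns consent-based against automatic referral. Separately, a first total of 10 with no other flag does not enter follow-up, although 10 counts as moderate at the repeat.

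**The case against.** Four points can fairly be made for the plan.

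**The promise is general.** Nothing says that the anxiety and self-harm criteria lapse at the repeat, so a mother still positive remains covered by the commitment to follow-up. This stands, and it is why the point is about missing content and timing. It does not fill the gap, because no action is attached to the commitment.

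**A two-week wait is not laid down for every mother.** A reader might infer that the protocol makes a mother with a positive self-harm answer wait 14 days before staff act. The documents do not support that as the stated rule: for a mother positive only on self-harm the timing is open, and the form invites same-day disclosure. What remains is that no timing is given.

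**A procedure may exist elsewhere.** Sections 7.1 and 7.2 rely on INFANT work instructions, and one may exist for this scale. Section 13 also allows emergency deviations to protect participants. Both are fair. But 7.4.3 cites no instruction, and freedom to depart from the protocol in an emergency is not a pathway. The point is therefore limited to 7.4.3 and the visible form.

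**The size is unknown.** A reader might take the protocol's estimate of up to 1 in 7 mothers, 200 / 7 = 28.6 or about 29 of 200, as the number affected. It is not: that figure concerns escalated scores in general and says nothing about low totals with a positive item. Likewise, the share of score values without an action is not a frequency, and many low totals carry no flag and need no action.

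**Conclusion.** The point holds as a gap in the written referral pathway that bears on participant safety, and it should be fixed. After the repeat, a mother still positive on self-harm with a total of 1 to 9, or still above 6 on anxiety with a total of 7 to 9, has no stated action beyond a general promise. For a mother positive only on self-harm, the timing and content of follow-up are unspecified from the start. Staff have no stated action on the day. The overlap at 13 and the mismatch between entry above 10 and a band starting at 10 are minor, but belong in the same correction.

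The self-harm range rests on items scored 0 to 3, which follows from the form and the stated maximum. The anxiety range rests on the plain-sum assumption. How many mothers would be affected cannot be derived from the documents. A reader might go further and conclude that the study has no safety procedure for these mothers; the documents do not show that, because unseen instructions may exist.

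**What to change.** Rewrite the paragraph in 7.4.3 as follows.

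- **On the day.** Staff already at the 4-month visit check item 10 before the mother leaves. Any score above 0 starts a GP referral route that day, whatever the total. Whether an immediate assessment is also needed, and in what form, is a clinical and resource decision for the responsible clinicians.
- **At the repeat.** An anxiety subscale above 6 or a self-harm item above 0 leads to a GP referral route, whatever the total.
- **Bands.** Make them exclusive (for example 10–12 and 13–30, or 10–13 and 14–30) and set entry at 10 or more, with the cut-offs confirmed by the responsible clinicians.

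If a work instruction already contains these steps, citing it in 7.4.3 is enough. Otherwise the cost is one rewritten paragraph and a matching staff instruction, submitted as an amendment, plus a brief check at the visit and some additional GP referrals, whose number the documents do not allow one to estimate.
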